8.1.7 Randomisation visit (V2)

Randomisation (V2) should take place within 14 days after the screening visit (V1). All results from screening assessments, including laboratory results, ECG and eye examination must be available, reviewed, dated and signed by the investigator and the in/exclusion criteria carefully reviewed to ensure subject eligibility prior to randomisation.

Randomisation of subjects will be done using IWRS, see Sections [10](#) and [11](#).

At V2 trial insulin products will be supplied to the subject after having completed the IWRS dispense call, see Section [10](#). Investigator or delegate staff will ensure proper training in trial product and pen handling. For subjects in the IGlar arm, the training must include pen differentiation. Directions for use (DFUs) will be provided to the subjects, refer to Section [8.6.3](#).

Hand-out of the DFU(s) to the subject must be documented in the subject's medical file.

At randomisation subjects must discontinue their pre-trial insulin, SU and glinides and the stop-date(s) must be recorded in the subjects' medical notes and transcribed into the eCRF. Treatment with other OADs should continue unchanged during the trial, see Section [5.4](#).

PRO questionnaires including baseline hypoglycaemia questionnaire (BHQ) must be completed by the subjects - please refer to Section [8.6.1](#).

For further details on trial procedures and assessments, refer to the Flow chart (Section [2](#)).

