8.6 Other Assessments

8.6.1 Patient reported outcomes

The PRO questionnaires must be completed by the subject without assistance of the site personnel. Instructions on how to complete the questionnaires will be provided to the subject.

The PRO questionnaires will be used to investigate the health related quality of life and diabetes treatment related impact.

The following PRO questionnaires will be supplied in addition to the diaries in a linguistically validated version in all languages relevant for this trial:

- **BHQ** is a questionnaire regarding the frequency of hypoglycaemic episodes and will be completed at baseline (randomisation visit (V2)) only.
- **SF-36v2®** Health Survey is a survey which assesses the subject's general health status and health-related quality of life utilising 36 questions covering eight concepts. The concepts cover: physical functioning, role-physical, bodily pain, general health, vitality, social functioning, role-emotional, and mental health over the prior four weeks. Scores for the eight concepts and two overall scores for the physical and the mental components are calculated.
- **TRIM-D** measures treatment related impact on subjects of diabetes medication across the spectrum of pharmacological treatment over the past two weeks. The TRIM-D consists of 28 items grouped into five domains. The domains are treatment burden (six items), daily life (five items), diabetes management (five items), compliance (four items) and psychological health (eight items). A total score and scores for the five domains are calculated.

The SF-36v2® and TRIM-D will be completed at the baseline (randomisation visit (V2)), prior to the intensification period (V28) and at the EOT visit (V40). These PRO questionnaires should be completed at the day of visit, preferably before any trial related procedures, except from fasting blood sampling, which may be done before.

Site staff is only allowed to write in the headers and on the front page of the questionnaires.

It is the responsibility of the investigator to review the questionnaires for completeness and possible AEs. To confirm that this has been done, the review must be documented by dated signature on the PRO questionnaires and/or in the subject's medical record. Care must be taken not to bias the subject.

If clarification of entries is needed, the subject should be questioned and a conclusion made in the subject's medical record. Care should be taken not to bias the subject.

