17.6 Health economics and/or patient reported outcomes

The following PRO endpoints are included in the trial:

Change from baseline to week 26 for:

- Health-related quality of life as evaluated by SF-36v2® Health Survey
- Treatment related impact as evaluated by the Treatment Related Impact Measure-Diabetes (TRIM-D)

Change from baseline to week 38 for:

- Health-related quality of life as evaluated by the SF-36v2® Health Survey
- Treatment related impact as evaluated by the TRIM-D

The domain and overall scores for both SF-36 and TRIM-D will be summarised descriptively based on observed data and explorative statistical analysis may be performed.

The data collected in the BHQ will not be included in the clinical trial report, nor will the data collected in the hypoglycaemic resource use interview questionnaire. Data from the latter will be used to assess costs associated with hypoglycaemia and provide information to be used in health economic analyses.

18 Ethics

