- Number of nocturnal, treatment-emergent severe or BG confirmed hypoglycaemic episodes during 26 weeks
- Number of treatment-emergent severe or BG confirmed hypoglycaemic episodes during 26 weeks
- Number of nocturnal, treatment-emergent severe or BG confirmed hypoglycaemic episodes during maintenance (week 16-26)
- Number of treatment-emergent severe or BG confirmed hypoglycaemic episodes during maintenance (week 16-26)
- Number of nocturnal, treatment-emergent severe or BG confirmed hypoglycaemic episodes during 38 weeks
- Number of treatment-emergent severe or BG confirmed hypoglycaemic episodes during 38 weeks

Data on treatment-emergent hypoglycaemic episodes are presented in terms of the number of subjects with at least one event (N), the percentage of subjects with at least one event (%), the number of events (E) and the event rate per 100 years (R). Separate summaries are made by severity considering all confirmed hypoglycaemic episodes, nocturnal confirmed hypoglycaemic episodes and the ADA classification of hypoglycaemia.

In addition, to the extent where data allows, the following endpoints are analysed statistically.

During 26 weeks:

- Number of nocturnal, treatment-emergent severe or blood glucose (BG) confirmed symptomatic hypoglycaemic episodes during 26 weeks
- Number of treatment emergent severe or BG confirmed symptomatic hypoglycaemic episodes during 26 weeks
- Number of nocturnal, treatment emergent severe or BG confirmed symptomatic hypoglycaemic episodes during maintenance (week 16-26)

- Number of treatment emergent severe or BG confirmed symptomatic hypoglycaemic episodes during maintenance (week 16-26)

During 38 weeks:

- Number of nocturnal, treatment emergent severe or BG confirmed symptomatic hypoglycaemic episodes during 38 weeks
- Number of treatment emergent severe or BG confirmed symptomatic hypoglycaemic episodes during 38 weeks

For endpoints addressing the hypoglycaemic rate in the 26 weeks or the 38 weeks period, a negative binomial model will be used, including treatment, previous insulin treatment regimen, previous OAD treatment, sex, and region as factors and age as covariate. The model will use a log-link function and the logarithm of the time period in which a hypoglycaemic episode was considered treatment emergent as offset. The treatment rate ratios will be estimated and 95% confidence intervals will be calculated.

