The rationale for investigating the hypoglycaemic rate during the maintenance is to reflect long term use, as prior to this period (the titration period) the glycaemic control might be unstable. For endpoints addressing hypoglycaemic rate in the maintenance period, subjects that discontinue randomised treatment during the maintenance period will contribute with the available data from the maintenance period. For subjects that discontinue randomised treatment during the 16 week titration period, the number of events in the maintenance period will be imputed based on data from the maintenance period for subjects that discontinued randomised treatment during the maintenance period. For these subjects, the number of events will be imputed corresponding to a 10 weeks maintenance period as follows:

- In the first step, 1000 samples from the posterior distribution of model parameters are extracted. The model is fitted to the on-treatment maintenance data for subjects that discontinued randomised treatment during the maintenance period for each treatment arm separately. This is done using a Bayes negative binomial log-link model with the same factors, covariates and offset as in the analyses of hypoglycaemic episodes described above. The 1000 samples are used as sampled parameter estimates in the next step.
- For each sample of model parameters, the total number of hypoglycaemic events in the maintenance period for subjects that discontinued randomised treatment in the titration period is imputed as a random number of events from a negative binomial distribution using the sampled parameters.
- For each of the 1000 imputed data sets, that now have maintenance period data for all randomised subjects, the mean treatment ratio is estimated using the same negative binomial model as in the analyses of hypoglycaemic episodes described above.

- The estimates and standard deviations for the 1000 imputed data sets are pooled to one estimate and associated standard deviation using Rubin's formula. From these the 95% confidence interval for the treatment ratio and the associated p-value are calculated.

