If the above model cannot fit due to sparse data, the model in step 1 is fitted to the on-treatment data for subjects that discontinued randomised treatment during either titration or maintenance, i.e. do not complete the scheduled 26 weeks of treatment. If this model cannot fit either, factors will be left out one by-one in the model using data from all subjects discontinuing randomised treatment before week 26 in the following order, until a model fits:

- sex
- age
- region
- previous insulin treatment regimen
- previous OAD treatment

The analyses and data presentations of hypoglycaemic events will be based on the hypoglycaemic episode form.

Classification of Hypoglycaemia:

Hypoglycaemic episodes are recorded by the subjects in their trial diaries throughout the trial. The information collected includes PG before treating the episode and whether the subject was able treat him/herself. This information is used by Novo Nordisk to classify episodes according to the confirmed hypoglycaemia definition and the ADA definition (severe, documented symptomatic, asymptomatic, probably symptomatic and pseudo).

- Treatment-emergent: hypoglycaemic episodes will be defined as treatment-emergent if the onset of the episode occurs on or after the first day of trial product administration, and no later than 7 calendar days after the last day on trial product
- Nocturnal hypoglycaemic episodes: episodes occurring between 00:01 and 05.59 both inclusive.
- Hypoglycaemic episodes are classified according to the Novo Nordisk classification of hypoglycaemia (see [Figure 2-1](#)) and the ADA classification of hypoglycaemia (see [Figure 2-2](#)).

[figure not shown]
Novo Nordisk classification of hypoglycaemia

In normal physiology, symptoms of hypoglycaemia occur below a plasma glucose level of 3.1 mmol/L (56 mg/dL)⁴. Therefore, Novo Nordisk has included hypoglycaemia with plasma glucose levels below this cut-off point in the definition of BG confirmed hypoglycaemia.

Novo Nordisk uses the following classification (see [Figure 2–1](#)) in addition to the ADA classification:

- Severe hypoglycaemia according to the ADA classification⁵
- Symptomatic BG confirmed hypoglycaemia: An episode that is BG confirmed by plasma glucose value <3.1 mmol/L (56 mg/dL) **with** symptoms consistent with hypoglycaemia.
- Asymptomatic BG confirmed hypoglycaemia: An episode that is BG confirmed by plasma glucose value <3.1 mmol/L (56 mg/dL) **without** symptoms consistent with hypoglycaemia.

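### Should the hypoglycaemia rate models have adjusted for the baseline hypoglycaemia questionnaire?

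*SAP*

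**What the plan says.** SAP 2.5.2 (Hypoglycaemic episodes) and Protocol 17.5.2 give the same model for the 26- and 38-week rates: negative binomial, log link, log of treatment-emergent time as offset, "including treatment, previous insulin treatment regimen, previous OAD treatment, sex, and region as factors and age as covariate". In the SAP this model serves four endpoints: all and nocturnal severe or BG confirmed symptomatic episodes, each over 26 and 38 weeks. The two all-episode counts are marked as key supportive endpoints in Protocol 4.2.2.2.

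Protocol 8.6.1 says the BHQ "is a questionnaire regarding the frequency of hypoglycaemic episodes and will be completed at baseline". Protocol 8.1.7 makes it mandatory at that visit: "PRO questionnaires including baseline hypoglycaemia questionnaire (BHQ) must be completed by the subjects". Protocol section 15 has it double-entered.

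Protocol 17.6 then states: "The data collected in the BHQ will not be included in the clinical trial report". SAP 2.6 repeats the sentence.

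The maintenance-period imputation in SAP 2.5.2 uses "a Bayes negative binomial log-link model with the same factors, covariates and offset as in the analyses of hypoglycaemic episodes", so it takes over the same covariate list.

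**The concern.** Past hypoglycaemia is a natural candidate predictor of future hypoglycaemia. Here a measure of it is compulsory, collected once at baseline and already entered, yet the models ignore it. The contrast with SAP 2.5.1 sharpens the impression: continuous endpoints are adjusted for their own baseline value, while the hypoglycaemia counts have no such term. Protocol 17.6 gives a purpose for the resource-use interview but none for the BHQ.

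At stake would be the width of four confidence intervals, two of them for key supportive safety endpoints. If the omission also biased the rate ratios, it would be an error and not merely a loss of precision.

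**Working it through.** **1. Does the omission break a rule of the plan?** No. The own-baseline rule in SAP 2.5.1 covers continuous endpoints; counts have their own model in 2.5.2. The exclusion of BHQ data stands in both documents. No precision target, power or hypothesis is set for hypoglycaemia, and these analyses are planned only as far as the data permit.

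**2. Inputs.** From the documents: 264 per arm and 15% discontinuing or missing (SAP 2.2). The only sample-size figure is for HbA1c, and it reproduces. With margin 0.40, adjusted difference 0.06 and SD 1.3, the normal formula gives 2 × 1.3² × (1.960 + 1.036)² / 0.34² ≈ 262.5 per arm, so 526 in total. The t-based version gives 528, with power 0.851 at 264 per arm. Hypoglycaemia rate, dispersion, BHQ recall period and correlation with on-trial episodes are not given, so everything below on precision is assumed.

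**3. Is the rate ratio biased without the covariate?** Negative binomial fits were simulated with 264 per arm, 15% stopping early at random and 300 runs per setting.

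- True ratio 0.80: mean estimate 0.785–0.811 without the covariate and 0.790–0.810 with it.
- True ratio 1.00: 1.013 and 1.009.

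The omission does not move the estimate.

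**4. What precision could be gained?** With mean count μ per subject and dispersion k, approximately

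Var(log RR) = 2(1/μ + k)/264.

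A covariate explaining a share R² of the dispersion replaces k by k(1 − R²). For μ = 1 and k = 2:

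- no covariate: √(2 × 3/264) = 0.151
- R² = 0.10: √(2 × 2.8/264) = 0.146, a fall of 3.4%
- R² = 0.30: √(2 × 2.4/264) = 0.135, a fall of 10.6%

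Over μ of 0.25–10 and k of 1–6, the fall is 1.0–5.0% at R² = 0.10 and 3.0–16.0% at R² = 0.30.

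A second simulation kept the SAP's other covariates in the model and used a recalled count as the BHQ stand-in, with log-normal heterogeneity and 200 trials per setting. Nocturnal episodes ("episodes occurring between 00:01 and 05.59 both inclusive") were given 6/24 = 25% of the rate. Mean standard errors, if the other covariates explain none of the heterogeneity:

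| Setting | Planned | With BHQ | Fall |
|---|---|---|---|
| 26 weeks, all, 3 per year, 26-week recall, correlation 0.7 | 0.1257 | 0.1154 | 8.2% |
| 38 weeks, same | 0.1165 | 0.1057 | 9.3% |
| 26 weeks, nocturnal, 0.75 per year, 26-week recall, 0.7 | 0.1853 | 0.1770 | 4.5% |
| 38 weeks, nocturnal, same | 0.1629 | 0.1537 | 5.6% |
| 26 weeks, all, 1 per year, 4-week recall, 0.5 | 0.1673 | 0.1665 | 0.5% |

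**5. Is the BHQ a clean baseline value?** The trial is open-label, and the documents do not show that the BHQ is answered before allocation is known. Protocol 8.1.7 fixes no order. In Protocol 8.6.1 the sentence "These PRO questionnaires should be completed at the day of visit, preferably before any trial related procedures" directly follows the one on SF-36v2 and TRIM-D and most naturally refers to those two. The BHQ has its own entry, which names the visit only. For the investigator's check, "the review must be documented by dated signature on the PRO questionnaires" (or in the medical record), and no completion time is required. Order therefore need not be recoverable afterwards.

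If one arm recalls 25% more because allocation is known, the adjusted rate ratio is multiplied by 0.909–0.993. Root-mean-square error of the log rate ratio at 26 weeks (600 trials per setting):

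| Setting | Planned | Adjusted, equal recall | 10% more | 25% more |
|---|---|---|---|---|
| 3 per year, 26-week recall, 0.7 | 0.1404 | 0.1215 | 0.1279 | 0.1550 |
| 1 per year, 4-week recall, 0.5 | 0.1757 | 0.1759 | 0.1754 | 0.1765 |

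In the first row the change runs from a 13.5% fall (0.0189/0.1404) to a 10.4% rise (0.0146/0.1404). In the second there is essentially none. The planned model does not use the BHQ and carries no such risk.

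**6. Knock-on effect.** Because the maintenance imputation borrows the covariate list, a new term would pass into it unless barred. That model is fitted per arm to subjects who stop in weeks 16–26. If the assumed 15% stop evenly over 26 weeks, that is 264 × 0.15 × 10/26 = 15.2 subjects per arm.

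**The case for a change.** The strongest reply is that a compulsory questionnaire on the very subject of these endpoints has no stated use. A planned model and a BHQ-adjusted model could be reported side by side at little cost, before database lock. At the favourable end, a standard error 8–9% lower is worth about 19–22% more subjects (1/0.918² = 1.19; 1/0.907² = 1.22). SAP 2.5.2 also plans no sensitivity analysis for these four ratios.

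Part of this stands. The gain cannot be dismissed as small: it is undetermined, and could exceed 10% if the BHQ were strongly prognostic. The planned intervals also depend on the negative binomial variance form. Where the simulated heterogeneity was heavier-tailed than that form allows, coverage of the unadjusted 95% interval ranged from 87% to 95%. In the first recall setting above, the model-based standard error (0.1257) sat about 10% below the actual error (0.1404). This also means that percentage falls in standard error are only a rough guide to accuracy.

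None of it shows that the plan is wrong. The BHQ's items, recall period, response format and episode definition are not in the documents, so a covariate could not be specified from them. It may not match the severe or <3.1 mmol/L symptomatic definition. Protocol 8.4.8 itself treats details of episodes documented more than seven days late as less reliable. Making the adjusted model the main analysis would require evidence on completion order that the protocol does not ask for. The realistic result is one more sensitivity analysis on four supportive endpoints. Adding a covariate late also has a credibility cost, since under Appendix A, sections 4 and 5, the sponsor reviews product-specific doses and hypoglycaemic episodes during the trial.

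**Conclusion.** The concern does not hold. The models omit baseline hypoglycaemia frequency, as observed, but this follows a choice stated in both documents and breaks no rule of the SAP. It leaves the rate ratios unbiased and does not touch the primary endpoint or the sample size. Adjustment could lower the standard error by roughly 0.5% to 9.3% in the settings tabulated here, and by up to 16.0% in the simpler formula at R² = 0.30. It could also raise the error by about 10% if recall differed by 25% between arms. All these figures rest on assumed rates, heterogeneity, recall periods and correlations.

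That the rate ratios are sound without the BHQ rests on randomisation, and on time on treatment not being related to hypoglycaemia propensity differently by arm. Whether to use a recalled covariate of uncertain timing in an open-label trial is a trade-off on which competent statisticians may differ.

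### The fallback imputation for week 16–26 hypoglycaemia pools titration and maintenance data without a period term

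*SAP*

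**What the plan says.** SAP 2.5.2 (Safety endpoints, Hypoglycaemic episodes) analyses weeks 16–26 separately to reflect long-term use, "as prior to this period (the titration period) the glycaemic control might be unstable". Subjects who stop randomised treatment during the 16-week titration period have no maintenance data, so a 10-week count is imputed for them from maintenance-period data. Step 1 keeps to that: "The model is fitted to the on-treatment maintenance data for subjects that discontinued randomised treatment during the maintenance period for each treatment arm separately". It uses a "Bayes negative binomial log-link model with the same factors, covariates and offset" taken from the main hypoglycaemia analysis, which is described as "including treatment, previous insulin treatment regimen, previous OAD treatment, sex, and region as factors and age as covariate". Since the fit is by arm, the treatment term falls away.

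The fallback opens with "If the above model cannot fit due to sparse data". In that case "the model in step 1 is fitted to the on-treatment data for subjects that discontinued randomised treatment during either titration or maintenance", meaning everyone who does not complete 26 weeks on treatment. The restriction to maintenance data is no longer stated. If this model also fails, sex, age, region, previous insulin regimen and previous OAD treatment are removed one at a time, with the pooled data kept.

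Protocol Amendment 1, section 2.16, has the same fallback. SAP section 3 lists no change to it.

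**The concern.** Subjects who stop in titration contribute almost only titration time, and subjects who stop in maintenance bring 16 titration weeks each if all their on-treatment data are used. The log-time offset corrects for length of exposure. It does not correct for an event rate that differs between the periods. One pooled rate would therefore be used to draw ten weeks of maintenance events, and the endpoint would take in the period it was built to leave out.

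If rates differ between the periods, each arm's maintenance rate is distorted. If the period effect or the share of subjects imputed also differs between arms, the treatment rate ratio is distorted too. Some difference by arm is conceivable. In Appendix A the comparator arm has a separately titrated IAsp dose (sections 3.3 and 3.5.2), and subjects on more than once-daily basal insulin transfer to the two arms under different starting rules (sections 3.1 and 3.2).

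**Working it through.** **Inputs from the documents.** 264 subjects per arm and 15% stopping treatment or having missing data by week 26 (SAP 2.2); a 16-week titration period and a 10-week maintenance period (SAP 2.5.2). The documents give no figure for the make-up of the fallback data.

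**Check of the stated sample size.** Distance to the margin 0.40 - 0.06 = 0.34, SD 1.3, one-sided 2.5%, t-test: power is 0.8507 at 264 per arm and 0.8494 at 263. The 264 is reproduced.

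**Assumptions.** The whole 15% is taken as stopping, which is an upper bound because the figure includes missing data. Rates are constant within each period, and the pooled model is approximated by a simple person-time rate. The titration-to-maintenance rate ratio, *r*, is varied.

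**1. Lower bound on the titration share (plain reading).** A subject stopping at week *x* ≤ 26 gives min(*x*, 16) titration weeks and max(*x* - 16, 0) maintenance weeks. The titration share is smallest at *x* = 26: 16/26 = 62%. Titration time is therefore the majority under any stopping pattern.

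**2. Uniform stopping over 26 weeks (assumed).**
- Stoppers per arm: 264 × 0.15 = 39.6. In titration: 39.6 × 16/26 = 24.37. In maintenance: 39.6 × 10/26 = 15.23.
- Titration weeks: 24.37 × 8 + 15.23 × 16 = 438.6.
- Maintenance weeks: 15.23 × 5 = 76.2.
- Titration share: 438.6/514.8 = 85% (84% with the 7-day on-treatment tail).

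**3. Other patterns and readings.**
- 10% stopping in weeks 0–12 and 5% in weeks 12–26: 88%.
- All stopping in maintenance, uniformly: 16/(16 + 5) = 76%.
- Narrower reading, in which maintenance stoppers give only maintenance data, with uniform stopping: 195.0/(195.0 + 76.2) = 72%. On this reading the share falls below half only if fewer than 5/13 = 38% of stoppers stop in titration.

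**4. Effect on an arm's rate (uniform stopping).** Imputed rate divided by maintenance rate: *k* = 0.852*r* + 0.148. The imputed share of the arm is 24.37/264 = 9.2%.

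| *r* | *k* | Change in arm rate, 0.0923 × (*k* - 1) |
|---|---|---|
| 0.5 | 0.574 | -3.9% |
| 0.8 | 0.830 | -1.6% |
| 1.5 | 1.426 | +3.9% |
| 2 | 1.852 | +7.9% |

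Under the 10%/5% pattern the range for *r* from 0.5 to 2 is -5.1% to +10.1%.

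**5. Effect on the treatment rate ratio.** With *c* completers, *m* maintenance stoppers and *t* titration stoppers, the relative arm rate is (10*c* + 5*m* + 10*t·k*)/(10*c* + 5*m* + 10*t*).
- Equal stopping and equal *r*: no shift.
- 20% against 10% stopping, *r* = 0.5 in both: 0.9455/0.9733 = 0.971, a shift of -2.9%.
- 20% against 10% stopping, with *r* = 0.4 against 0.8: 0.9346/0.9893 = 0.945, a shift of -5.5%.
- An extreme contrast, 15% stopping in both arms with *r* = 0.5 against 2: 0.9595/1.0810 = 0.888, a shift of -11%. This needs period effects in opposite directions in the two arms.

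**The case against.** The branch is a contingency. About 15 maintenance stoppers per arm rests on assumed uniform stopping and an upper-bound 15%. Whether a Bayesian model fails to fit depends on priors and a failure criterion that the SAP does not give. A reader might infer that the fallback will probably be used. Small donor numbers, an arm-specific model with five covariates and a nocturnal endpoint make that plausible, but the documents do not establish it.

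A reader might also infer that the SAP itself declares titration time unrepresentative. It does not. It says only that "prior to this period (the titration period) the glycaemic control might be unstable", and it gives no event rates by period, so neither the presence nor the direction of bias is shown.

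Nor do the arms follow wholly different titration rules. The unit steps for IGlar (Appendix A, Tables 1 and 2) and IDegAsp OD (Tables 3 and 4) are identical. The differences lie in IAsp titration and the starting-dose transfer.

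The effect is small against sampling error. If the mean is 0.2 to 1.0 events per 10 weeks and the negative binomial dispersion is 2 to 4 (assumed), the standard error of the log rate ratio, √[2(1/mean + dispersion)/264], is about 0.15 to 0.26. Shifts of 3% to 5.5% are then about 0.1 to 0.4 standard errors.

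Finally, the fallback keeps discontinuers as donors for discontinuers. A period factor would have to be estimated from the same sparse maintenance data that triggered the fallback.

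All of this limits the size and likelihood of the problem. It does not supply the missing period term. Nor does it explain why titration data are added before any covariate is dropped.

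**Conclusion.** The point stands as a correctable inconsistency in a contingency rule. Applied as written, the fallback imputes week 16–26 counts from a data set that is at least 62% titration time on the plain reading, about 85% under uniform stopping and 72% on the narrower reading with uniform stopping. Step 1 and the stated rationale for the endpoint call for maintenance data.

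The size rests on assumed period rate ratios and stopping patterns: about -4% to +8% on an arm's rate for ratios of 0.5 to 2, and about 3% to 5.5% on the treatment rate ratio in the moderate scenarios with differences between arms. It is zero when the arms have the same period effect and imputed share.

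Reach is limited to the two statistically analysed maintenance endpoints (all, and nocturnal, severe or BG confirmed symptomatic episodes). Both are supportive and neither is marked key. The primary HbA1c analysis and the 26- and 38-week hypoglycaemia analyses do not use this imputation. The change is worth making because it removes an avoidable source of bias at little cost, not because a trial conclusion is known to be at risk.

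**What to change.** Amend the fallback paragraph of SAP 2.5.2 as follows.

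1. If step 1 cannot be fitted, first drop covariates in the order already listed, keeping to on-treatment maintenance data from maintenance-period discontinuers.
2. Only if that still fails, add the titration data. Split each donor's record at week 16. Include a period factor (titration or maintenance) that is never dropped, log time at risk within the period as offset, and a subject random effect, because one donor can now supply two correlated records. Draw the imputed counts at the maintenance level.
3. State the priors and what counts as failure to fit, so that the move from one stage to the next is fixed before database lock.

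There is a precedent. The superseded maintenance model in Protocol 17.5.2, replaced by Amendment 1, also combined both periods, and it carried a period factor with interactions and a subject random effect.

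The cost is a few sentences, minor programming and a somewhat wider imputation variance. With very few maintenance events among discontinuers, the period factor will be imprecise, and the report should say so. Borrowing the period ratio from all on-treatment subjects would assume that completers and discontinuers share it. That moves away from the SAP's use of discontinuers as donors and should be at most a sensitivity analysis.
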